### **Specific Aims**

The purpose of this study is to determine if a customized therapy, Acoustic Coordinated Reset (CR) Neuromodulation (also referred to as Desyncra) reduces tinnitus-related distress with comparable efficacy as for Cognitive Behavioral Therapy (CBT) for people who have bothersome tinnitus.

### **Inclusion Criteria**

- Age  $\geq 18$  years
- Primary and persistent tinnitus [defined by AAO-HNSF guidelines (Tunkel et al, 2014); 6 months or longer in duration]
- Tonal tinnitus
- Dominant tinnitus frequency measured between 0.2 and 10 kHz
- Tinnitus Questionnaire (TQ) score  $\geq 30$  at screening (to confirm moderate to severe tinnitus)
- No current participation in other tinnitus therapy program
- Willing and able to listen to the acoustic prescription for 4-6 hours daily during the trial
- Able to pass the Tone Audibility Assessment with factor of 1.1

### **Exclusion Criteria**

- Secondary/somatic tinnitus due to a suspected underlying disease (defined by AAO-HNSF guidelines)
- Atonal, pulsatile, intermittent, or occasional tinnitus (determined by self-report and by the Tinnitus Screener)
- Any hearing threshold  $> 70$  dB HL from .25-8 kHz, unless subject passes the Tone Audibility Assessment screening with a factor of 1.1
- Any health or other problems that may prevent the person from completing the study procedures as determined by investigator
- Participant reports current (within the past week) suicidal ideation and/or homicidal ideation
- Use of medication that may trigger tinnitus [e.g., quinine derivatives, aminoglycoside antibiotics, daily high dose non-steroidal anti-inflammatory drugs  $\geq 1000$  mg, salicylates (when not prescribed as a low dose for cardiac health), loop diuretics and chemotherapy agents like cis-platin] at the discretion of the Principal Investigator
- Conductive hearing loss defined as an air-bone gap of 15 dB or greater at more

than two frequencies in one ear

- Visible congenital or traumatic deformity of the ear
- History of active drainage from the ear within the past 90 days
- History of sudden or rapidly progressive hearing loss within the past 90 days
- Inability to read and respond appropriately to instructions that appear on the computer screen, and/or to perform all of the study procedures

**Desyncra Group.** Subjects randomized to the Desyncra group will be fit with the devices. The Research Audiologists will be trained by a Desyncra representative to dispense the Desyncra for Tinnitus Therapy System according to company guidelines. The devices are fitted and programmed based on the subject's tinnitus characteristics and hearing ability at the first visit and the subject will use the device for 4-6 hours per day for 24 weeks.

In the case of a subject reporting his/her tinnitus has completely vanished, the subject will be instructed to reduce the amount of time using the therapy device to 1 hour per day. In the event that the tinnitus perception comes back, the subject would increase the amount of time using the device back to 4-6 hours per day.

If a subject's tinnitus characteristics become outside the range where tinnitus is treatable (e.g., too-high or too-low tinnitus pitch), the clinician may stop therapy for up to 2 weeks. Any changes in the therapy schedule will be documented accordingly.

**CBT Group.** Subjects randomized to this group will receive CBT consistent with best practice guidelines. Subjects will attend 6 CBT therapy sessions over the course of 8 weeks following baseline performed by a psychotherapist as per the recommendations outlined in the AAO-HNSF guideline (Tunkel et al 2014).

### **Step-by-Step Guidance on Conducting the Study**

#### **Recruitment**

- Post ads at the VA Portland Health Care System (VAPORHCS; e.g., audiology, primary care, women's health clinics) and in the surrounding community
- Place ads in newspaper (paper and/or online); post online advertising; contact previous participants who consented to contribute their information into data repositories
- Mail recruitment letters to health care clinics and facilities in Oregon and Washington (USA)

#### **Telephone Screening**

- Screen candidates over the phone using screening script; if eligible, gather information from candidate and schedule initial appointment

#### **Visit 1: In-Person Screening/Baseline**

- Administer informed consent

- HIPAA authorization
- Administer questionnaires
- Study staff may opt to use the Sound Finder with candidates (classifies tinnitus as tonal vs. noisy perception)
- Audiologic testing
- Tinnitus pitch matching procedure using procedure specified by Desyncra Inc.

**Visit 2 (1 week after screening completed, approximately ±1 week)**

- All subjects will complete the pitch matching procedure and questionnaires
- Subjects in the Desyncra group will have their device adjusted according to manufacturer guidelines
- Subjects in the CBT group will complete their 1st CBT session
- Subjects are paid \$40 for attending the visit

**Follow-up to Visit 2 for subjects randomized to the Desyncra arm**

- An audiologist will call subjects randomized to the Desyncra arm approximately 1 to 2 weeks after Visit 2 to follow-up and see how the subject is doing with the sound-based therapy

**Visit 3 (4 weeks after screening completed, approximately ±1 week)**

- All subjects will complete the questionnaires
- Subjects in the Desyncra group will complete the pitch matching procedure and have their device adjusted according to manufacturer guidelines
- Subjects in the CBT group will complete their 4th CBT session
- Subjects are paid \$40 for attending the visit

**Visit 4 (8 weeks after screening completed, approximately ±2 weeks)**

- All subjects will complete the pitch matching procedure and questionnaires
- Subjects in the Desyncra group will have their device adjusted according to manufacturer guidelines
- Subjects in the CBT group will complete their 6th and final CBT session
- Subjects are paid \$40 for attending the visit

**Visit 5 (16 weeks after screening completed, approximately ±2 weeks)**

- All subjects will complete the questionnaires
- Subjects in the Desyncra group will complete the pitch matching procedure and have their device adjusted according to manufacturer guidelines
- Subjects are paid \$40 for attending the visit

**Visit 6 (24 weeks after screening completed, approximately ±2 weeks)**

- All subjects will complete the pitch matching procedure and questionnaires
- All subjects will complete an exit interview
- Subjects in the Desyncra group will discontinue use of the device
- Subjects are paid \$40 for attending the visit

### **Visit 7 (28 weeks after screening completed, approximately $\pm 2$ weeks)**

- All subjects will complete the pitch matching procedure and questionnaires
- Subjects are paid \$40 for attending this final visit
- Desyncra group will have the opportunity to keep their devices
- CBT group will have the opportunity to be fit with and receive the Desyncra device
- Any participant who keeps the Desyncra device will be given information on how to receive assistance from a local provider or company representative for device-related concerns

### **Statistical Analysis Plan**

A Bayesian approach to the analysis of outcome data will be used. Based on simulations across several conditions, we anticipate requiring a total of no more than 200 subjects to have at least 80% power to identify a significant benefit of Desyncra therapy compared to CBT.

Data from this study will be provided to the NCRAR Data Manager who will develop and maintain a database with all study data. Either the Data Manager or other study personnel (e.g. Research Assistant) will enter the data. The Data Manager will perform double entry of the data and check for any errors, which will be remediated. After the study is complete and all data are entered and verified, the Data Manager will conduct preliminary analyses of the data to determine if there are any differences in outcomes between groups. These analyses will be overseen by the NCRAR Biostatistician who will conduct further analyses as necessary.

A preliminary analysis will be conducted after a total of ~30 subjects have been randomized and completed the 16 week follow-up visit. The first formal interim analysis will be conducted after a total of ~30 subjects have been randomized and completed the 24 week follow-up visit or ~16 subjects per treatment arm. A second formal interim analysis will occur after a total of ~72 subjects have been randomized (~31 subjects per treatment arm) and completed the 24-week follow-up. The primary endpoint of this study occurs 24 weeks after being dispensed the Desyncra device at which time the primary outcome measure, the TQ, is repeated.

The efficacy of Desyncra will be assessed by contrasting the Desyncra and CBT subjects' change from baseline on the TQ outcome. The  $\delta$  parameters describe the overall change from baseline common to both treatment arms. The  $\phi$  parameters describe the benefits of Desyncra over CBT in this study. We assume that the TQ observations are Gaussian random variables with population mean defined above plus a subject-specific random intercept  $\theta_i$ , and with residual standard deviation  $\sigma$ .

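### The aim is comparable efficacy to CBT, but the only power statement is for a benefit over CBT, and the available text gives no margin or rule for comparability

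*Combined protocol and SAP*

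**What the plan says.** Specific Aims gives a single purpose: to find out whether Desyncra "reduces tinnitus-related distress with comparable efficacy as for Cognitive Behavioral Therapy (CBT" in people with bothersome tinnitus.

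The Statistical Analysis Plan gives the only sample-size statement. It sets a ceiling of 200 on total enrolment, taken from simulations whose conditions are not listed. The power claimed for that ceiling is "at least 80% power to identify a significant benefit of Desyncra therapy compared to CBT".

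The rest of that section follows the same line. "A Bayesian approach to the analysis of outcome data will be used"; efficacy is judged by "contrasting the Desyncra and CBT subjects' change from baseline on the TQ outcome"; and the φ "parameters describe the benefits of Desyncra over CBT in this study". The primary endpoint is the TQ at 24 weeks. The section plans a preliminary analysis of about 30 subjects at 16 weeks, then formal interim analyses at about 30 and about 72 subjects with 24-week data.

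From Specific Aims to the end of the Statistical Analysis Plan there is no non-inferiority or equivalence margin, no region of practical equivalence, no posterior threshold and no stopping rule.

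**The concern.** Showing that two treatments are comparable and showing that one beats the other are different hypotheses with different success rules. The first needs a margin: how much worse (or how different) Desyncra may be and still count as comparable. The second needs a threshold on the probability that φ favours Desyncra. The plan states the first as its aim and powers the second.

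What is at stake depends on which was meant.

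- **Comparability meant.** The 80% power belongs to another question. If the therapies really are similar, the powered conclusion will rarely be reached. With no margin fixed, *comparable* would have to be defined after results are known, and the planned early looks give several occasions to see them first.
- **Superiority meant.** The analysis section is coherent in direction, but the aim is worded wrongly. A trial that fails to show a benefit could then be reported as having met an aim of comparable efficacy, which a non-significant superiority result does not establish.

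**Working it through.** **1. The plan's own figure.** It cannot be reproduced. It comes from Bayesian simulations, and the text gives no effect size, SD, prior, threshold or dropout. It can only be back-solved. Assume 1:1 allocation (100 per arm), a normal approximation, two-sided 5%, no dropout, no interim looks, and effects in units of the between-subject SD of TQ change:

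- SE = √(2/n) = √(2/100) = 0.1414 SD
- effect with 80% power = (1.960 + 0.842) × 0.1414 = 0.396 SD

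Under these assumptions, 200 subjects with 80% power corresponds to a true Desyncra advantage of about 0.40 SD.

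**2. What 200 subjects could show for comparability.** Same SE, true difference 0, assumed margin m:

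- non-inferiority, one-sided 2.5%: power = Φ(m/SE − 1.960)
- equivalence, two one-sided 5% tests: power = 2Φ(m/SE − 1.645) − 1, set to 0 if negative

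| Margin (SD) | m/SE | Non-inferiority | Equivalence |
|---|---|---|---|
| 0.40 | 2.828 | Φ(0.868) = 81% | 2Φ(1.184) − 1 = 76% |
| 0.30 | 2.121 | Φ(0.161) = 56% | 2Φ(0.476) − 1 = 37% |
| 0.20 | 1.414 | Φ(−0.546) = 29% | 0% |

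The margin with 80% power is 0.396 SD for non-inferiority. For equivalence it is (1.645 + 1.282) × 0.1414 = 0.41 SD, or (1.960 + 1.282) × 0.1414 = 0.46 SD if each test is at 2.5%.

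**3. Sensitivity (non-inferiority, same three margins).**

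- 20% dropout (80 per arm, SE = √(2/80) = 0.158): 72%, 48%, 24%.
- No dropout, random-intercept model with a common baseline mean and an assumed baseline to follow-up correlation of 0.4 (SE = √(0.02 × 0.7) = 0.118): 92%, 72%, 39%.

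The answer moves more with the unstated margin than with either of these.

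**4. Chance of declaring a benefit if the therapies are equal.** Assume a flat prior and a posterior threshold of 0.975 or 0.95 (none is stated).

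- Single look: 1 − threshold = 2.5% or 5%.
- If both formal interims could also declare a benefit at the same unadjusted threshold: the three z-statistics at 30, 72 and 200 subjects have correlations √(30/72), √(30/200) and √(72/200). The probability that at least one exceeds 1.960 is about 6%; for 1.645 it is about 11%.
- The per-arm counts in the same section (about 16 and 31, so 32 and 62 in total) give the same rounded figures.

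These are the false-positive rates of a superiority rule. They show how seldom the powered conclusion would be reached under equality; they do not measure the mismatch itself.

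**The case against.** The strongest defence is that *comparable efficacy* is a loose phrase in what is really a superiority trial. The power target, and φ described as a benefit over CBT, both point that way. That reading is plausible, and the documents do not rule it out. On it, the loss of the 80% power and the after-the-fact definition of *comparable* do not follow. What remains is a misworded aim and the risk of misreporting a null result.

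A second defence is that the rule may sit in text not available here. The front matter was removed, and the model's mean, described as already defined, is not shown. So the absence of a margin or rule can be asserted only for the text seen. The conflict between the two statements does not depend on missing text, since both are present.

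Third, φ is a between-arm contrast and its posterior could serve either question. That is right, and the model is not at fault. But an estimate without a rule fixed beforehand does not settle what counts as comparable.

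A reader might infer more than this supports:

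- **That 200 subjects are too few.** The documents give no margin or SD. Under the assumptions above, 200 is adequate for non-inferiority at about 0.40 SD or wider.
- **That this is a non-inferiority trial with the wrong analysis.** The text does not settle which question was intended.
- **That the missing posterior threshold is itself the fault.** Alone, it would be missing detail. It matters here because the aim and the power statement conflict on the primary question.

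**Conclusion.** The concern holds in this limited form: the aim as written and the hypothesis that was powered are different questions, and the available text has no margin or rule for comparability.

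Its weight depends on intent. It is a should-fix if superiority is meant, because one sentence of the aim is wrong and could mislead the report. It is a must-fix only if comparability is the intended conclusion, because the trial would then have no stated power and no stated success rule for its primary question.

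No single number measures the fault. The power figures rest on assumed margins in SD units, a true difference of 0, equal allocation and a normal approximation. The 2.5–5% and 6–11% figures rest on an assumed flat prior and assumed thresholds, and the higher pair also on unadjusted claims at both interims. They are illustrations, and the case does not depend on them.

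**What to change.** Make Specific Aims and the Statistical Analysis Plan state the same question before any between-arm look, including the 16-week preliminary analysis.

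**If superiority is meant (the cheaper route).** Reword the aim as superiority of Desyncra over CBT on TQ change at 24 weeks. State the posterior threshold on φ at 24 weeks that the existing simulations used, and tie the 80% power to it. Add a sentence that failing to reach the threshold will not be reported as comparable efficacy. Cost: a wording change, one stated threshold and a check of simulations already done.

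**If comparability is meant.** Say that the 80% figure does not apply to that aim. Fix a justified margin Δ in TQ points and a posterior rule, for example P(φ at 24 weeks > −Δ) ≥ 0.975 with φ coded so that positive values favour Desyncra; if equivalence is meant, the rule must bound both sides. Rerun the simulations with a true difference near 0 and the expected dropout, and restate the power at 200.

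The second route costs more than a rerun. The margin is open to debate, and a tight one would carry clearly lower power at 200. Under the assumptions above, 80% non-inferiority power would take about 350 subjects in total at 0.30 SD and 786 at 0.20 SD. The sponsor would have to justify a wider margin, accept and report the lower power, or enrol more.

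### Does the device-dispensing clock in the primary endpoint sentence, or the unnamed week-28 contrast, call for a change to the plan?

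*Combined protocol and SAP*

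**What the plan says.** The Statistical Analysis Plan fixes the endpoint in time by stating that "The primary endpoint of this study occurs 24 weeks after being dispensed the Desyncra device", when the TQ is administered again. The visit schedule runs on a different origin. Its 24-week visit is headed "Visit 6 (24 weeks after screening completed, approximately ±2 weeks", and all subjects, in both arms, complete questionnaires at it.

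The two treatments have different lengths. For Desyncra, "the subject will use the device for 4-6 hours per day for 24 weeks" (Desyncra Group paragraph), and at Visit 6 "Subjects in the Desyncra group will discontinue use of the device". For CBT, "Subjects will attend 6 CBT therapy sessions over the course of 8 weeks following baseline" (CBT Group paragraph), with the sixth and last session at the visit headed "Visit 4 (8 weeks after screening completed, approximately ±2 weeks".

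Visit 7, at 28 weeks from screening (±2), again has all subjects complete questionnaires. At that visit "CBT group will have the opportunity to be fit with and receive the Desyncra device". The Statistical Analysis Plan mentions 16-week and 24-week follow-up but not Visit 7. It describes the change parameters (delta) and the Desyncra-benefit parameters (phi) in the plural, and refers back to a mean model whose equation is not in the text available for review.

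**The concern.** Two things look wrong.

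First, a two-arm contrast needs a time origin that both arms share. Device dispensing is not one: a CBT subject has no device before week 28 and may never take one. Applied as written, the sentence would leave the primary endpoint undefined in the comparator arm.

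Second, the week-24 contrast compares subjects nominally finishing a course of daily device use with subjects whose therapy ended months before. On its own it cannot separate a lasting effect from one present only while the device is in use. Visit 7 is the only scheduled assessment after the device stops, and the statistical prose assigns it no analysis. If that stays open, how a week-28 result is used could be decided after the data are seen. In addition, Visits 6 and 7 are each timed from screening, so the time off device at Visit 7 could vary widely between subjects.

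**Working it through.** **Inputs (weeks after screening, from the visit headings).** Visit 2: 1 ± 1, so 0 to 2. Visit 4: 8 ± 2, so 6 to 10. Visit 6: 24 ± 2, so 22 to 26. Visit 7: 28 ± 2, so 26 to 30. The plan gives no figure of its own for this point. Its sample size and power statement does not bear on it, and cannot be rebuilt without an effect size, a standard deviation and a success threshold.

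**1. The literal reading fails at once.** A CBT subject fitted at Visit 7 would reach the endpoint at 28 + 24 = week 52, when the last visit is week 28. A CBT subject who declines the device would never reach it. No one could run the trial that way.

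**2. The operational reading is unambiguous.** Visit 6 is a common 24-week visit with questionnaires in both arms. The interim-analysis paragraph of the Statistical Analysis Plan counts subjects who have completed 24-week follow-up in each treatment arm, so its authors use a visit that CBT subjects also attend.

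**3. The two clocks nearly agree in the Desyncra arm.** The Desyncra Group paragraph places fitting at the first visit.
- If dispensing coincides with completion of screening, Visit 6 falls 22 to 26 weeks after it, which is the Visit 6 window itself.
- If dispensing were as late as Visit 2 (an assumption), the range is 22 − 2 = 20 to 26 − 0 = 26 weeks.

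**4. Time since treatment.**

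| Interval | Nominal | Shortest | Longest |
|---|---|---|---|
| Last CBT session to Visit 6 | 24 − 8 = 16 | 22 − 10 = 12 | 26 − 6 = 20 |
| Device stop to Visit 7 | 28 − 24 = 4 | 26 − 26 = 0 | 30 − 22 = 8 |
| Last CBT session to Visit 7 | 28 − 8 = 20 | 26 − 10 = 16 | 30 − 6 = 24 |

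The 0 and 8 in the second row need the same subject to sit at opposite ends of two windows. They are bounds, and the documents give no distribution between them.

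**5. Can the week-28 contrast be estimated as things stand?** Yes, if the Visit 7 questionnaires include the TQ. That is an inference, because the visit text does not name the instrument. It is a strong one, since Visit 6 uses the same wording and the TQ is known to be repeated there. With a random intercept per subject, a phi for each visit, n per arm in equal arms and complete data, the intercept cancels and SE(phi28 − phi24) = sigma × sqrt(4/n). At n = 100 (half the stated maximum of 200) this is 0.20 sigma. Sigma is not stated, so this shows that the contrast can be estimated, not that it would be precise enough.

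**6. Would tying Visit 7 to the actual Visit 6 date help?** Suppose Visit 7 were set 4 ± 1 weeks after Visit 6, borrowing the tolerance in the heading "Visit 3 (4 weeks after screening completed, approximately ±1 week". The off-device interval would narrow to 3 to 5 weeks. The visit would then fall between 22 + 3 = 25 and 26 + 5 = 31 weeks from screening, instead of 26 to 30. One spread shrinks and another grows, at a visit that is not primary. Time off treatment would still differ between arms: nominally 4 weeks against 20.

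**The case for a change.** The best case for a change is that this sentence defines the trial's primary endpoint, that it is wrong for one arm, and that correcting it takes one line. For week 28, a parameter in a model is not an analysis role: even if the equation contains a phi for that visit, the prose does not rank it, and further analyses are left to the biostatistician's judgement. Visit 7 is the only point at which persistence off the device can be seen, so leaving it unranked invites selective emphasis.

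Part of this stands. The dispensing phrase is wrong as worded, and the available prose does not name week 28. A reader should therefore give a persistence claim less weight than the week-24 result unless its role was fixed beforehand.

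The rest does not carry. The wording slip misleads no one who reads the visit schedule, and correcting it moves no assessment and no estimate. The Specific Aims concern reduction of tinnitus-related distress and state no durability aim, so a persistence analysis would be an addition and not the repair of an error. The missing equation also prevents any firm statement that the plan omits week 28.

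**Conclusion.** No change follows. The dispensing clock is a clerical slip with one workable reading: change from baseline in TQ at Visit 6 in both arms. The week-24 contrast is a defensible fixed-time comparison of two treatment strategies of different length, and should be read as such: the device course just ending against CBT nominally 16 weeks finished (12 to 20 across windows). The documents give neither a direction nor a size for any bias in it.

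The week-28 point is a gap that analysts can fill from data already scheduled, by estimating the Visit 7 contrast in the same model and reporting the observed time off device (nominally 4 weeks, bounds 0 to 8). Retiming Visit 7 would trade one spread for another without equalising time off treatment.

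This rests on three assumptions: that Visit 6 is the visit meant for both arms, which the schedule and the per-arm counts support; that the TQ is among the Visit 7 questionnaires; and that actual visit dates are recorded. If the TQ is not collected at Visit 7, the week-28 contrast cannot be formed, but the primary comparison is unaffected.
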